4 STUDY VARIABLES

4.1 Pharmacokinetic variables

4.1.1 Primary pharmacokinetic variables

The primary PK variables will comprise $C_{max},\,t_{max},\,AUC_{\tau},\,and\,CL/F_{ss}$ obtained from the plasma concentration-time profiles for PSL:

AUC_r: area under the curve over a dosing interval (12 hours) tion and and CL/F_{ss}: apparent total clearance at steady-state 4.1.2

The secondary PK variable will be the trough plasma concentration of MHD (OXC metabolite) before, during, and after dosing to steady state with PSL.

Additionally, the secondary PK variables for PSL metabolites (and

) will comprise C_{max} , f_{max} , AUC_{τ} , and the ratio of metabolite to PSL based on

AUC_τ.

4.2.12

90CU

Other pharmacokinetic variables 4.1.3

The following other PK variables will be assessed during the study:

- Trough plasma concentrations of LEV, LTG, or BRV before, during, and after dosing to steady state with **PSL**
- Comparison of plasma concentrations from MITRA microsampling (dried blood) with • venous sampling for PSL

Safety variables 4.2

Secondary safety variables

The following secondary safety variables will be assessed during the study:

Incidence of AEs and SAEs

4.2.2 Other safety variables

The following other safety variables will be assessed during the study:

Changes in vital signs (pulse rate [PR], respiratory rate [RR], SBP, and DBP)

- Changes in clinical laboratory test results (hematology, serum chemistry, and urinalysis)
- Changes in 12-lead ECG parameters

Study description This is a Phase 1, multicenter, open-label study in study participants with epilepsy, to evaluate the effect of OXC on the PK and safety and tolerability of PSL. A total of 28 study participants will be evaluated in the following ? per group): Group 1 (In J

- Group 1 (Inducers): study participants on stable therapy with OXC (at least 1200mg/day either as monotherapy or adjunctive to LEV, LTG, or BRV). Oxcarbazepine may be used as monotherapy (at least 7 study participants) or in combination with 1 or more of LEV, LTG, or BRV). (For adjunctive therapy, the dosing of each AED in the combination [OXC+LEV, OXC+BRV, or OXC+LTG] must be within the range used per label.)
- Group 2 (Neutral [control]): study participants on stable therapy with LTG (at least 150mg/day monotherapy or adjunctive to LEV or BRV, LEV (at least 1g/day monotherapy or adjunctive to LTG), or BRV (up to 200mg/day adjunctive to LTG). Lamotrigine or LEV may be used as monotherapy (at least 7 study participants) or in combination with each other. Brivaracetam may only be used in combination with LTG. (For adjunctive therapy, the dosing of each AED in the combination [LTG+LEV or LTG+BRV] must be within the range used per label.)

Padsevonil will be dosed to steady state (4.5 days) in both groups and the effect of background therapy on PSL PK will be assessed at steady state.

5.2 **Study Periods**

Screening Period 5.2.1

The Screening Period consists of a single Screening Visit, which will be conducted at the unit within 28 days prior to check-in for the Treatment Period, and a Baseline Visit, which will be conducted at the unit 1 day prior to the Treatment Period.

A sufficient number of study participants with epilepsy will be screened to ensure that 14 study participants are included in each group.

BRV). (For adjunctive therapy, the dosing of each AED in the combination [OXC+LEV, OXC+BRV, or OXC+LTG] must be within the range used per label.) In Group 2 (study participants) monotherapy (at least 7 study participants) or in combination with 1 or more of LEV, LTG, or

monotherapy (at least 7 study participants) or in combination with each other. Brivaracetam may only be used in combination with LTG. (For adjunctive therapy, the dosing of each AED in the combination [LTG+LEV or LTG+BRV] must be within the range used per label.)

5.2.1.1 Screening Visit (Day -28 to Day -2)

Study participants are required to sign a written Informed Consent form (ICF) prior to the ations thereof conduct of any study-related procedure. Screening assessments will be conducted, after which the eligibility of study participants will be determined based on: inclusion and exclusion criteria (see Section 6.1 and Section 6.2, respectively); demographics; medical history; full physical examination (including weight and height); medication history; vital sign measurements; several laboratory tests (hematology, serum chemistry, urinalysis, serology screening, alcohol breath procedures. A serum pregnancy test will be performed to assess eligibility for women of childbearing potential. test, and urine toxicology screen); triplicate 12-lead ECGs; and recording of AEs/medical isions

5.2.1.2 **Baseline Visit (Day -1)**

At the Baseline Visit, study participants will check in at the unit the afternoon prior to the visit and receive a study participant Identification Card.

The following procedures/assessments will be repeated: inclusion/exclusion criteria verification; medical history; full physical examination; medication history; vital sign measurements; laboratory tests (hematology, serum chemistry, urinalysis, alcoholoreath test, and urine toxicology screen); triplicate 12-lead ECGs; and recording of AEs/medical procedures. A urine pregnancy test will be performed to assess eligibility for women of childbearing potential. Study participants will also be assessed with the Columbia-Suicide Severity Rating Scale (C-SSRS) to assess suicidal risk.

Study participants can then be discharged from the unit after all procedures/assessments have been completed. The study participants may continue being confined to the unit at the Investigator's discretion or continue the study ambulatory until the afternoon of Day 7.

Treatment Period 5.2.2

The Treatment Period consists of 3 days of dose titration (Day 1, Day 2, and Day 3), 4.5 days of PSL maintained at a stable dose (Days 4 through 7 and the morning of Day 8), and 4.5 days of dose taper (evening of Day 8 and Days 9 through 12).

5.2.3 Safety Follow-Up Period

Study participants will be discharged on Day 13 and return for an End of Study (EOS) Visit on Day 20±1.

The SFU Period consists of discharge from the unit on Day 13 and an EOS Visit performed on Day 20±1 or upon discontinuation of the study. Study participants will have the following procedures/assessments completed at the EOS Visit: C-SSRS; a full physical examination; prior and concomitant medication; vital sign measurements; laboratory safety (hematology, serum chemistry, and urinalysis); triplicate 12-lead ECGs; and recording of AEs/medical procedures. A urine pregnancy test will also be administered for woman of childbearing potential.

5.3 Pharmacokinetic sampling

Study participants will undergo serial blood sampling to measure plasma concentrations of PSL, PSL metabolites (________ and _______), and OXC metabolite (MHD), as well as safety monitoring. Blood samples for plasma concentrations of LEV, LTG, and BRV samples will be collected and stored during the study; they will only be measured on an as-needed basis. Pharmacokinetic analysis will be performed using both conventional plasma as well as contemporaneous MITRA microsampling (dried blood) of PSL to compare the 2 methods.

5.3.1 Venous blood

Venous blood samples for PK analysis will be collected as follows:

- Padsevonil and PSL metabolites (
 - prior to the morning dose of PSL on Day 1 through Day 7 and Day 9 through Day 13

and

):

- prior to the morning dose of PSL and 0.25h, 0.5h, 1h, 1.5h, 2h, 3h, 4h, 6h, 8h, and 12h after administration of the morning dose of PSL (prior to the evening dose) on Day 8
- AEDs: trough samples prior to the morning dose of the AED(s) on Day -1, Day 1 through Day 13, and the EOS Visit

5.3.2 Microsamples of capillary blood

Samples for PK of PSE from a finger skin prick will be collected using the MITRA device, as close to the conventional PK sampling as possible, at each of the time points identified for the venous blood samples for Day 8 in Section 5.3.1.

5.4 Study duration per study participant

The maximum total duration of the study is 49 days (7 weeks) for each study participant, including the Screening Period (up to 28 days), Treatment Period (12 days), and the SFU Period (maximum of 9 days).

The end of the study is defined as the date of the last visit of the last study participant in the study.

hisdoci

<section-header><section-header><section-header><text><text>

UCB Clinical Study Protocol			Padsevonil				SHOLIN SL	08 June 2018 UP0070
Table 5-1: Schedule of study a	assessmen	ts					017E11	
Procedures	Screenin	g Period		Treatme	nt Period	7-10	SFU P	eriod
	Screening	Baseline	Titration	Maint	enance	Taper	SFU Post- treatment	EOS/ET ^a
	Day -28 to Day -2	Day -1	Days 1-3 (Ti1-Ti3)	Days 4-7 (M1-M4)	Day 8 ° (M5/(Tal)	© Days 9-12 ° (Ta2-Ta5)	Day 13	Day 20 (±1)
Written Informed Consent	X				PUR			
Record info on habits and lifestyle	X			01.				
Demographics & baseline characteristics	X		To	SIIdde				
Inclusion/Exclusion criteria verification	Х	Х		U				
General medical/procedures history	X	X						
Enrollment to Inducers or Neutral (control) Group		X	UINE					
Study Participant Identification Card assigned		X	0					
Psychiatric History	Х							
Administer C-SSRS ^b	°2	X	X°	X°			Х	Х
Physical examination	, X	Х					Х	Х
Prior and concomitant medications	, S O				×			
Record intake of grapefruit, starfruit, or pawpaw (as beverage, fruit, or supplements) ^d	2		X	Х	X	Х		
Blood sample for MHD plasma level $^\circ$	Х	Х	Х	Х	Х	Х	Х	Х
Pregnancy test f	Х	Х						Х
Confidential Societa		ц	age 24 of 69					

. . .

	Protocol
	Study
UCB	Clinical

Padsevonil

018 100070 100070

EOS/ET^a

Period

20 (±1) Day

×

 \varkappa ×

× ×

 \succ \Join

 \varkappa

K 6

0

×

× \varkappa

 \mathbf{X}^{h}

×

0

) X

 \mathbf{X}^{h} ×

 \approx

 \varkappa

Table 5-1:	Schedule of study a	Issessmen	S					
Procedures		Screening	g Period		Treatme	nt Period	1,0	SFU F
		Screening	Baseline	Titration	Mainto	enance	Taper	SFU Post- treatment
		Day -28	Day -1	Days	Days	Day *	🖉 Days	Day
		to Day -2		1-3	4-7	8	9-12 ^e	13
				(Ti1-Ti3)	(M1-M4)	(M5/Ta1)	(Ta2-Ta5)	
Hematology, s urinalysis	erum chemistry,	Х	Х			DUR		Х
Serology (HIV	', Hepatitis B & C)	Х			100			

Vital signs^g

Height/weight, BMI 12-lead ECG^g

Recording of adverse events/medical Drug/alcohol screen

 \varkappa ×

procedures

Admit to study center

Discharge from study center Dispense Padsevonilⁱ

210000ms 0; Blood sample for AED trough level ^j Study drug accountability

×

×

×

 \varkappa

 \varkappa

×

 \succ

 \varkappa

×

 \mathbf{X}^{k}

 \mathbf{X}^{k} \varkappa

Ň

X

 \mathbf{X}^{k}

 \varkappa

×

 \Join

×

×

Nog Nog Blood sampling for PSL and metabolites PK levels

Final Disposition Determination

AED=antiepileptic drug; BML=body mass index; C-SSRS=Columbia-Suicide Severity Rating Scale; ECG=electrocardiogram; EOS/ET=End of Study/Early Termination; h=hour(s); HW=human immunodeficiency virus; IMP=investigational medicinal product; M=Maintenance; Mono Hydroxy Derivate; OXC=oxcarbazepine; PK=pharmacokinetic(s); PSL=Padsevonil; SFU=Safety Follow-Up; Ta=Taper; Ti=Titration

Page 25 of 69

Confidential OCUTIV

UCB Clinical Study Protocol	Padsevonil	08 June 2018 UP0070
Note: Day –1 is defined as the day before Day 1. Da Note: For study participants prematurely terminating terminating from the study should be encouraged t last dose of study drug.	y 1 is defined as the first day of administration. g or completing the study, final disposition is recorded at EC to undergo final evaluation procedures, in accordance with t	DS/ET. All study participants prematurely the EOS/ET schedule, as soon as possible after the
Note: Study participants will be admitted to the unit assessment (6h). They will be readmitted to the un of all procedures/assessments. During visits on Da dose and remain until completion of all procedures	on the afternoon prior to Day -1 for baseline assessments an it on the afternoon of Day 7 and will be discharged from the y 1 through Day 7, ambulatory study participants to will co basessments. They should return to the unit at least 1 hour	nd can be discharged after the last ECG e unit on Day 13 in the morning after completion me to the unit at least 2 hours prior to the morning prior to the evening dose
^a The SFU assessments should be performed for any ^b At the Baseline Visit, complete the "Baseline/Scre ^c Only for ambulatory study marticipants	A study participant who withdraws from the study 7 to 9 day ening" version of the C-SSRS. At all other visits, complete	is after the last dose of PSL.
d Grapefruit, starfruit, and participants. ^d Grapefruit, starfruit, and pawpaw (as beverage, fru throughout the study will not be allowed. If this is window.	it, or supplements) within 72 hours before first administrati the case at the start of the study, study participation may be	ion of IMP, during the Treatment Period, and delayed as long as it occurs within the screening
^e This is only done for study participants taking OX prior to the morning dose of OXC. If the study par At the Screening Visit, the blood sample must be c	C. If the study participant administers OXC in the morning ticipant administers OXC once daily, then the blood sample collected no later than on Day -7 (with MHD reassessment, or later than Day - 2	and evening, the blood sample should be obtained e should be obtained just prior to the daily dose. if required, no later than Day -4); other safety
f A serum pregnancy test will be performed at Scree EOS/FT for women of childbearing potential only	sning for women of childlearing potential only. A urine pre-	gnancy test will be performed at Baseline and at
^g Triplicate 12-lead ECGs and vital signs (after a recollection prior to the morning dose of PSL.	st of at least 5 minutes at 2, to 3-minute intervals) will be pe	erformed on Days 1 through 12, prior to the PK
^h Triplicate 12-lead ECG (after a rest of at least 5 m points at Day 8: predose, 0.5h, 1h, 2h, 3h, 6h, and triplicate 12-lead ECGs will be performed after a r 0.5h, 1h, 2h, 3h, and 6h postdose for the morning a	inutes at 2- to 3-minute intervals) will be taken shortly prior 12h post the morning dose of PSL. In addition, 1 day prior test of at least 5 minutes at 2- to 3-minute intervals for each administration of PSL, and 0.5h predose for the evening administration of PSL.	r to each of the following PK collection time to the first dose of PSL on Day -1 (Baseline) of the following matching time points: predose, ministration of PSL, where dosing time is
equivalent to the expected time of dosing on Day 8 Investigational medicinal product will be administ	s. ered bio 12h apart each day. All study participants enrolled	into the study will receive 1 day of PSL at
100mg bid (Day 1) followed by 2 further days at 2 and once on Day 8 in the morning. A dose taper we PSL 200mg. Padsevonil 200mg bid will be admini	Uting bid (Day 2 and Day 3). Padsevonil 400mg will then the bill be initiated on the evening of Day 8, when study particip stered on Day 9 and Day 10. Padsevonil 100mg bid will be	be administered orally bid on Day 4 through Day 7 bants will be administered an evening dose of administered on Day 11 and Day 12.
^j Obtain blood samples for storage; measurement of concomitant AED in the morning and evening, the morning dose of PSL). If the study participant adm	^c the trough level of the concomitant AED will be done as n is blood sample should be obtained prior to the morning dose initisters the concomitant AED once daily, then the blood sa	eeded. If the study participant administers the of the AED (and on applicable days, prior to the unple should be obtained just prior to the daily
dose (and it applicable, prior to the dose of PSL). ^k Obtain blood samples (venous only) for measurem On Day 13, sampling should occur prior to dischai	ient of trough levels of PSL and metabolites just prior to the see.	e morning dose of PSL on Day 1 through Day 12.
So FUSUINO		
Confidential	Page 26 of 69	

¹ Obtain blood samples (venous and MITRA) for 1 0.25h, 0.5h, 1h, 1.5h, 2h, 3h, 4h, 6h, 8h, and 12h 4h samples; ±10min for the 6h, 8h, and 12h samp	r measurement of plasma concentration of PSL at the following time:	
	2h postdose. Time windows for postdose samples are as follows: $\pm 5 \text{m}$ mples. The 12h sample must be obtained prior to the evening dose.	s: predose (within 5mm of dosing), then at nin for the 0.25h, 0.5h, 1h, 1.5h, 2h, 3h, and
	" Alle D	ISLIDIA
	UE LOIRESIICICE	
	BAIEUI AUE HOUD	
S'OJ DOSSI OG JOULUES JUSU		
Confidential South	Page 27 of 69	

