8.1.2 Baseline Visit (Day -1)

sions or variations thereof. Study participants will check in to the unit on the afternoon prior to this visit and will be assigned their Study Participant Identification Card. The following procedures/assessments will plication and be performed before discharge:

- Inclusion/exclusion criteria verification
- General medical/procedures history
- Enrollment to Inducers or Neutral (control) Group
- Dispense Study Participant Identification Card •
- C-SSRS ("Baseline/Screening" version of the C+SSRS) • autho
- Full physical examination •
- Prior and concomitant medications •
- Vital signs (including PR, RR, SBP, DBP, and oral temperature)
- **Triplicate 12-lead ECGs**
 - Morning: approximately 0.5h prior to the expected time of the morning dose on Day 8, and 0.5h, 1h, 2h, 3h, and 6h after the expected time of the morning dose on Day 8
 - Evening: approximately 0.5h prior to the expected time of the evening dose on Day 8
- Blood samples (venous) for trough PK analysis (prior to AED morning dose):
 - MHD plasma level (only for study participants taking OXC)
 - AED trough level (for storage)
- Blood and urine samples for the following clinical laboratory tests will be collected:
 - Hematology, serum chemistry, and urinalysis
 - Urine pregnancy test (for women of childbearing potential only)
 - Urine drug screen
- Alcohol breath test
- Recording of AEs/medical procedures

there of.

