10.7.3 Standard 12-lead ECG

Triplicate standard 12-lead ECGs (RR interval, PR interval, QRS interval, QT, QTcB, and QTcF) will be recorded at times specified in Table 5-1, according to the following procedure: study participant lies in a supine position for >5 minutes; then a 12-lead ECG wilk be recorded in the same position. All ECG recordings will be performed in triplicate at 2- to 3 minute intervals.

Electrocardiograms will be recorded at a speed of 25mm/s and with a calibration of 1cm/mV.

The purpose of the enhanced ECG monitoring procedures in this study is to match the observed ECG parameters with the contemporaneous plasma levels of PSL as closely as possible, at key time points during Day -1 (no exposure) and Day 8 (anticipated peak exposure). This will support an evaluation of any relationship between exposure to PSL and changes in key ECG parameters, most particularly QT intervals.

As specified in Table 5-1, a Baseline ECG series will be performed on Day -1. On this day, triplicate standard 12-lead ECGs will be performed for each of the following time points, intended to match as closely as possible the timing of the PK sampling series planned for Day 8: 0h, 30min, 1h, 2h, 3h, 6h and the pre-evening dose PK sample. On Day 8, a matching series of ECGs will be performed predose, 30min, 1h, 2h, 3h, and 6h after the morning dose of PSL, and approximately 30min before the evening dose, as close as possible to the time of the pre-evening dose PK sample. On Day 1 through Day 12, except Day 8, the triplicate standard 12-lead ECG will be performed prior to the morning dose of PSL, again timed to match as closely as possible to the time of the predose PK sample being taken. Care should be taken to record the timing of each ECG and PK sample as accurately as possible, to enable the precise evaluation of their temporal relationship.

By decision of the sponsor and the Investigator, the time points specified in Table 5-1 may be modified based on preliminary safety and PK assessments from the study.

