12.4.3 Vital signs and ECGs

Vital sign variables (PR, RR, SBP, and DBP) and changes from Baseline (predose on Day 1) will be summarized at each time point by group. Frequency tables of values outside the normal ranges will be produced by treatment group and time point.

Electrocardiograms will be recorded 3 times at each time point. The individual mean at each time point will be calculated as raw parameters for descriptive analysis. The 12-lead ECG parameters (RR interval, PR interval, QRS interval, QT, QTcB, and QTcF) and change from Baseline (time-matched Baseline on Day -1) will be descriptively summarized at each time point by group. Baseline per time (0h, 0.5h, 1h, 2h, 3h, 6h) at Day -1 is defined as the value of the corresponding time-matched measurements of the ECG parameters. Frequency tables of values outside the normal ranges will be produced by group and time point.

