3.2.2 Study periods

For each subject completing the study, the expected maximum duration of participation will be approximately 49 days with a maximum of 12 days exposure to investigational product, and will consist of the following periods:

Screening Period (Day -28 to Day -2)

The Screening Period consists of a single Screening Visit, which will be conducted at the unit tions thereof within 28 days prior to check-in for Treatment Period, and a Baseline Visit, which will be conducted at the clinical research unit (CRU) 1 day prior to Treatment Period. Study participants will check-in at the CRU on Day -1.

Treatment Period (Day 1 to Day 12) •

The Treatment Period consists of 3 days of dose titration (Day 1, Day 2, and Day 3), 4.5 days of PSL maintained at a stable dose (Days 4 through 7 and the morning of Day 8), and 4.5 days of dose taper (evening of Day 8 and Days 9 through 12). Details are given in Table 3-2.

The SFU Period consists of an End of Study (EOS) Visit performed on Day 20 ± 1 after discharged on Day 13 or upon discontinuation of the study.

The end of the study is defined as the date of the last visit of the last subject in the study.

3.3 **Definition of Baseline values**

In general, Baseline will be the last non-missing value prior to dosing. Scheduled or unscheduled measurements can be used as the Baseline value.

Measurement-specific Baseline timepoints are presented in Table 3-1.

Measurement	Definition of Baseline
• Hematology, serum chemistry, urinalysis	Baseline or if missing the Screening value
Vital signs	Predose of treatment period. Treatment Period predose Day 1 or if missing Day -1. If Day -1 is missing the Screening value will be used. Otherwise baseline = Day -1 predose
• ECG	Time matched baseline at Day-1 at predose, 0.5h, 1h, 2h, 3h and 6h post morning dose of PSL on Day 1 and 0.5h predose of evening dose of PSL.
C-SSRS	Separate baseline questionnaire for C-SSRS.

Definition of Baseline Table 3–1:

ECG=electrocardiogram; C-SSRS= Columbia-Suicide Severity Rating Scale

If a measurement is repeated at Baseline or a given treatment period and is obtained prior to dosing in that treatment group, then the last available measurement will be used as the Baseline

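### The Table 5-1 note names the 6h ECG as the last on Day -1 and permits discharge after it, but the protocol and SAP require a further time-matched ECG about 5.5 hours later

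*Protocol*

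**What the plan says.** **Discharge on Day -1.** The note under Protocol Table 5-1 says participants come in on the afternoon before Day -1 and "can be discharged after the last ECG". The sentence continues on the next line of the extracted text: "assessment (6h). They will be readmitted". Read together, the last Day -1 ECG is the 6h one, and the next admission mentioned is Day 7. Two body sections set a different rule. Section 5.2.1.2 allows discharge once every procedure and assessment is complete. Section 8.1.2 heads its list of Baseline Visit procedures by saying they are done before discharge.

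**ECGs required on Day -1.**

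- Table 5-1 footnote h: predose, 0.5h, 1h, 2h, 3h and 6h, "and 0.5h predose for the evening" administration, using the dosing times expected on Day 8.
- Section 8.1.2: a morning series, then "Evening: approximately 0.5h prior to the expected time of the evening dose on Day 8".
- Section 10.7.3: "0h, 30min, 1h, 2h, 3h, 6h and the pre-evening dose PK sample".

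**Baseline for analysis.** SAP Table 3-1 defines the ECG baseline as time-matched on Day -1 and includes "0.5h predose of evening dose of PSL". Protocol Section 12.4.3 lists only the earlier times: "Baseline per time (0h, 0.5h, 1h, 2h, 3h, 6h) at Day -1 is defined as" the time-matched value.

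**The concern.** Site staff are likely to work from the schedule table, and its note points to a discharge time that precedes a required assessment. Section 10.7.3 states what the Day -1 series is for: it is the no-exposure counterpart of the Day 8 series, so that ECG parameters, QT intervals above all, can be related to padsevonil exposure.

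Everyone is in the unit on Day 8, and Sections 8.2.3.1 and 10.7.3 schedule the pre-evening triplicate then, so the on-treatment value should be collected. Its matched baseline would be absent for anyone who left at 6h on Day -1. Once dosing starts it cannot be recovered.

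The SAP offers no clean repair. In Table 3-1 the laboratory and vital-sign rows have fallback values; the ECG row has none. SAP Section 4.2 rules out imputation in general. SAP Section 3.3 also carries general wording about using the last measurements before dosing, which could lead a programmer to substitute a value from another time of day. The result would then be a difference that is not time-matched, under a label saying that it is.

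**Working it through.** No figure in the plan needs reproducing. The check is schedule arithmetic and a comparison of sections.

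**Inputs**

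- Interval between morning and evening dose: 12h (Table 5-1 footnote i).
- Evening ECG on Day -1: about 0.5h before the expected evening dose time (footnote h; Section 8.1.2).
- ECG named as last in the note: 6h after the expected morning dose time (Table 5-1 note; reference time from Section 8.1.2).
- Planned participants: 28 (Protocol Section 12.8).

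**Timing**

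- Evening ECG after the expected morning dose: 12h − 0.5h = 11.5h.
- Gap from the discharge point in the note: 11.5h − 6h = 5.5h.

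**Share of the series**

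- Day -1 time points: predose, 0.5h, 1h, 2h, 3h, 6h and pre-evening = 7.
- Lost on discharge at 6h: 1 of 7, or 14% of the time points. In tracings, that is 3 of 7 × 3 = 21.
- Participants affected: 0 to 28. The documents do not say how many will go home on Day -1; Section 5.2.1.2 leaves confinement to the investigator's discretion.

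**Sections side by side**

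| Place | Last Day -1 ECG, or discharge rule |
|---|---|
| Table 5-1 note | 6h; may leave after it |
| Table 5-1 footnote h | 0.5h before expected evening dose |
| Protocol 5.2.1.2 | Leave only after all assessments |
| Protocol 8.1.2 | Evening ECG listed among procedures before discharge |
| Protocol 10.7.3 | Pre-evening time point |
| SAP Table 3-1 | Pre-evening time point is a matched baseline |
| Protocol 12.4.3 | Baseline times stop at 6h |

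The note disagrees with a footnote to its own table, with three protocol sections on conduct and with the SAP. Only the list in Section 12.4.3 also stops at 6h. No section tells a discharged participant to come back that evening. For ambulatory participants, the next attendance in the Table 5-1 notes is before the morning dose on Day 1.

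**The case against.** The strongest reply is that the protocol already states the right rule. Sections 5.2.1.2 and 8.1.2 make discharge wait for all assessments, footnote h schedules the evening ECG, and the note only permits discharge. On that view, what remains is an out-of-date time in brackets. This stands in part: it makes the loss conditional on a site following the note, so a reader who infers that discharged participants will necessarily lack the baseline goes beyond the documents. It does not remove the contradiction, because the note gives a specific hour where Section 5.2.1.2 gives a general condition.

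A second reply is that the impact is slight. ECG change is listed among the other safety variables, is summarised descriptively and is not tested. The times from predose to 6h stay matched, and observed Day 8 evening values can still be reported. This stands in full and limits the weight of the point.

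A third reply is that the short list in Protocol Section 12.4.3 changes nothing. SAP Section 1 applies the protocol unless the SAP specifies otherwise, and SAP Table 3-1 includes the evening time. This also stands; aligning the list is editorial.

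Two stronger readings are tempting but unsupported:

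- **Unequal eligibility screening.** A reader might infer that those sent home are screened on fewer ECGs. The QTc limit in exclusion criterion 16 works within a triplicate (2 of 3 recordings), and nothing says that every Day -1 time point feeds eligibility.
- **Bias between groups.** Missing values would follow who goes home. Group follows background antiepileptic drug, and the documents do not link the two.

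**Conclusion.** The point holds as an internal inconsistency in the schedule. The Table 5-1 note allows discharge about 5.5h before a Day -1 ECG that its own footnote h, Sections 8.1.2 and 10.7.3, and SAP Table 3-1 require, and it conflicts with the discharge rule in Section 5.2.1.2.

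If the note is followed, each participant discharged at 6h loses one of seven matched ECG baselines, and the Day 8 pre-evening change from Baseline cannot be computed as planned. The number affected lies between 0 and 28. The primary PK comparison is untouched.

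The size rests on three assumptions: expected dose times 12h apart, no return to the unit on the evening of Day -1, and no unmatched value put in place of the missing baseline. The scope is small, but a missed measurement cannot be recovered and the correction is simple, so the change should be made.

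**What to change.** Reconcile the Table 5-1 note with footnote h and Sections 5.2.1.2, 8.1.2 and 10.7.3. Replace 6h with the pre-evening ECG (about 0.5h before the expected evening dose time) as the last Day -1 assessment before discharge.

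As an editorial alignment, add the pre-evening time to the baseline list in Protocol Section 12.4.3 so that it agrees with SAP Table 3-1.

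The cost is two wording changes. Participants who go home would stay about 5.5h longer on Day -1 than the note now implies, for an assessment already in the schedule. No procedure is added.
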